8.1.3 Data Correction

Corrections to eCRFs will be prompted via automated electronic edit checks and queries manually created by reviewers. The corrections and the individual making the correction(s) to the eCRF will be within Clindex.

8.1.4 Investigator Regulatory Binder

Each Investigator must maintain an accurate, complete, and current copy of the Regulatory Binder. Upon receipt of copies of changes or revision updates to the Binder from the Sponsor, the Investigator will add the updated document to the Regulatory Binder and will mark the outdated portion of the Binder as "obsolete" by crossing a diagonal line across the page(s) along with date the page was made obsolete and the initials of the person performing the update. The outdated pages will be removed from their current section and filed in the "Protocol Amendment" section along with the Revision Log provided by the Sponsor. If an Investigator holds multiple copies of the Regulatory Binder, then all copies must be updated with the current revisions.

8.1.5 Study Correspondence

Each Investigator and all personnel from the investigational site will maintain records of all

correspondence, electronic, written, and consent, relating to any aspect of the clinical investigation. The records are maintained in the Investigator's Study Binder consisting of, but not limited to correspondence with other participating clinical investigators, the reviewing IRB, and the Sponsor. The Study Monitor will examine the contents of the correspondence.

8.1.6 Data Privacy

Subjects will be made aware that their personal data will be collected and processed in accordance with data protection legislation including the Health Insurance Portability and Accountability Act of 1996 (HIPAA). Subjects will be asked to sign an Authorization for Release of Personal Health Information (PHI) for the purpose of this investigation. This authorization may be combined with the ICF depending on local IRB preference. Results from the Clinical Investigation may be published. However, Subject confidentiality will be maintained at all times and it will not be possible to identify individual Subjects from any data presented.

Investigation Sites Outside of the US, Confidentiality will be maintained in accordance with provisions of the 1998 UK Data Protection Act or national transposition of the EU Data Protection Directive 95/46/EC or local equivalent legislation. Data protection consent will be obtained from the subjects as part of the informed consent process. Where applicable data protection submissions will be performed.

8.1.7 Record Retention, Inspection, and Custody

The PI must maintain all documentation related to the study until notified by the Sponsor. The PI will allow representatives of the Sponsor, IRB/EC, the FDA, or other government regulatory agencies to inspect all study records, eCRFs, and corresponding portions of the subject's office and/or hospital medical records at regular intervals during the study. These inspections are to verify adherence to the protocol, integrity of the data being captured on the eCRFs, and compliance with applicable regulations.

Subject medical records will be maintained in a confidential manner. Study reports will not identify subjects by name. These reports may be submitted to the FDA and/or regulatory authorities.

If custody of the records is transferred, notice of such a transfer should be given to the Sponsor no later than ten (10) working days after the transfer occurs.

The Investigator should retain copies of all documents pertaining to this clinical investigation (including source documentation, the informed consent document and any other documents to identify the subjects) for at least 2 years after this clinical investigation is completed. In addition, if the Clinical Investigator moves/retires, etc., he/she should provide AtriCure Inc. the name and address of the person who will look after and be responsible for the subjects' clinical investigation related records.

8.1.8 Medical Dictionary Coding

Medical dictionary coding will be performed using a coding thesaurus algorithm. The MedDRA will be used upon data entry and query resolution for AEs, SAEs, via automated and manual coding processes.

8.1.9 Data Quality Assurance

Quality control and quality assurance processes implemented during this study to ensure subject safety rights, and welfare are protected and to foster data integrity are characterized below.

8.1.10 Investigator Training

Protocol Specific Training

Training will be scheduled once IRB approval is obtained, and the Clinical Study Agreement is executed.

The training of clinical site personnel will be the responsibility of AtriCure, Inc. This procedure may only be performed by qualified investigators, familiar with the study procedures and techniques. A formal training program consisting of didactic and interactive sessions will be performed at each investigational site with participating investigators and study personnel identified at each site prior to subject enrollment. This **Investigator Training Plan** is described in **Appendix 3**.

The Investigator and the study staff will also be trained in general aspects of the procedure, study administration, content and manner of administration of the questionnaires, all procedures in the protocol, and the procedure for electronic data acquisition and transmission. Site personnel will be trained on the study protocol by the Sponsor through a combination of teleconferences, Web-Ex conferences and on-Site training, as appropriate. Training will be documented. It is ultimately the responsibility of the Investigator to ensure all clinical site personnel participating in this study are trained.

8.1.11 Monitoring

This study will be monitored by the sponsor to ensure:

- The rights and well-being of the subjects are protected;
- The reported study data is accurate, complete, and verifiable from source documents; and
- The conduct of the study is in compliance with the currently approved protocol/amendment(s), applicable GCPs, and with applicable local/regional regulatory requirements.

AtriCure, as Sponsor of this study, will be responsible for monitoring this study. The monitor's duties are to aid the Principal Investigator in the production and maintenance of complete, legible, well-organized and easily retrievable data. In addition, the monitor will be responsible for assuring the Principal Investigator understands the protocol and all applicable regulations. Approaches to monitoring include on-site visits and may include a remote visit, as appropriate and the rationale and frequency for monitoring will be at the Sponsor's discretion. The extent and nature of monitoring will be predetermined and based on considerations such as the objective, design, complexity, and endpoints of the study and mutually agreed to by the Sponsor. The frequency of monitoring will be determined for each site based on factors including: the planned enrollment, the rate of enrollment, and the current study conduct. Study conduct can be evaluated remotely based on compliance percentage, discrepancy rate and discrepancy type. Monitors will be trained on and comply with established standard operating procedures as well as a written monitoring plan specified by the Sponsor.

In order to perform the monitoring role effectively, the monitor must verify eCRF entries with source documents. The monitor must be given access to primary subject data which supports

the information recorded on the eCRF, i.e., hospital notes, appointment books, original laboratory records, etc. Access to these documents must also be given should the regulatory authority in the instance of an external inspection. Since a subject has the right to refuse access to these documents on the grounds of confidentiality, consent to access is included in the informed consent document, which the subject signs.

The Principal Investigator will receive reasonable notification prior to each monitoring visit during the course of this clinical investigation. The Principal Investigator will be expected to co-operate with the monitor at each visit for the review and verification of eCRFs and any additional records that may have been previously arranged between the Principal Investigator and the monitor.

8.2 Changes to Protocol, Protocol Deviations and Protocol Amendments

8.2.1 Changes to Protocol

The Investigator should not implement any deviation from, or changes of the protocol without agreement by the sponsor and prior review and documented approval/favorable opinion from the IRB/EC of an amendment, except where necessary to eliminate an immediate hazard(s) to study subjects, or when the change(s) involves only logistical or administrative aspects of the study (e.g., change in monitor(s), change of telephone number(s)). In the event of an emergency situation, the Investigator must notify the Monitor or AtriCure immediately. A full written report of the situation must be forwarded to the IRB/Ethics Committee who approved the original protocol and AtriCure within 10 working days of the event.

8.2.2 Protocol Deviations

The Investigator agrees to conduct the study in accordance with this protocol; however, protocol deviations may occur during the course of the study. Protocol deviations are events occurring during the conduct of the study which are not in compliance with the protocol and for which an amendment has not been granted. Protocol deviations can be committed by the Sponsor, the PI, or study subject. A deviation can be identified from a number of sources. Potential sources include but are not limited to a member of the PI's staff, the monitor during monitoring visits, or a member of the data management or statistical groups when entering or analyzing data. The PI or PI's representative are encouraged to contact the monitor or AtriCure as soon as possible upon observing a protocol deviation. Regardless of the source, it is crucial to document the deviation and record all corrective actions. Protocol deviations will be reported in the final report.

The process for capturing deviations will be detailed in the monitoring plan. The process will require that documentation describe the deviation, appropriate actions taken, and will be included in the study file for the respective PI and subject. The study site representative will be advised to record the deviation and relevant discussion with the Sponsor about the deviation in subject source documents.

Protocol deviations affecting the scientific soundness of the study or the rights, safety, or welfare of the subjects, will be reported by the PI, as required by the IRB/EC.

Protocol deviations will be summarized and grouped into relevant categories for analysis and may include, but not be limited to, subjects who:

- Entered the study although they did not satisfy the eligibility criteria; or
- Developed withdrawal criteria during the study, but not removed.

8.2.3 Protocol Amendments

If it becomes necessary to amend the protocol, then the nature of the amendment will be agreed between the Sponsor and the Principal Investigator(s) and this will be recorded with a justification for the amendment. The appropriate IRBs/EC will be informed of amendments prior to implementation of the change.

9.0 STATISTICAL METHODS

9.1 Clinical Study Objective

The objective of this study is to evaluate the effectiveness and safety of minimally invasive cardiac surgical ablation utilizing the AtriCure Bipolar System and AtriClip PRO LAA Exclusion System in a Dual Epicardial and Endocardial Procedure (DEEP) for the treatment of persistent or longstanding persistent AF. It is expected that this combined technology will provide a substantial increase in effectiveness over the current treatment options, with only a moderate increase in safety risk.

9.2 Primary Endpoints

9.2.1 Primary Effectiveness Endpoint

The primary effectiveness endpoint is freedom from any documented AF, atrial flutter, or atrial tachycardia lasting >30 seconds in duration (or for the entire length of a 30-second ECG tracing) through the 12-month follow-up visit in the absence of Class I or III AADs (with the exception of previously failed AADs at doses not exceeding those previously failed). Any arrhythmia that occurs within the blanking period or during the AAD optimization period, prior to the 6-month visit will not be considered a failure. The rhythm status used for evaluation of this endpoint shall be derived regularly scheduled monitoring as well as any symptom driven monitoring that is performed. For the purposes of this study, atrioventricular nodal reentrant tachycardia (AVNRT), inappropriate sinus tachycardia, and Wolff–Parkinson–White syndrome (WPW) will not be considered procedure failures.

The 12-month follow-up window utilized for this endpoint is based on time from the catheter ablation procedure. However, if a subject refuses the second stage of the DEEP procedure, i.e., the catheter ablation procedure, or experiences a safety event or medical condition precluding the catheter ablation procedure, every attempt will be made to continue collecting follow-up data, including their primary effectiveness status at 12 months after the surgical procedure (the 3-month blanking and AAD optimization periods measured from the surgical ablation procedure in this case). If their status cannot be ascertained, the endpoint will be missing, and thus subject to missing value methods below.

9.2.2 Primary Safety Endpoint

The primary safety endpoint is a composite endpoint consisting of any one or more of the following events if they are adjudicated by the CEC to be serious adverse events (SAEs) and related to device/procedures as follows:

1. AtriCure Bipolar System, AtriClip Pro LAA Exclusion System, within 30 days of the epicardial surgical ablation procedure; or

2. The epicardial surgical ablation procedure within 30 days following the epicardial procedure; or
3. The endocardial index procedure (or a repeat endocardial ablation procedure performed during the blanking period) within 7 days following an endocardial ablation procedure

Events except as otherwise specified for a particular condition include:

- a. death (regardless of cause)
- b. stroke
- c. transient ischemic attack (TIA)
- d. myocardial infarction (MI)
- e. pulmonary or systemic embolism
- f. pericarditis resulting in an effusion that leads to hemodynamic compromise or requires pericardiocentesis, prolongs hospitalization by more than 48 hours, requires a new hospitalization, or persists for more than 30 days following the ablation procedure
- g. excessive bleeding, defined as one or more of the following:
 - i. re-operation to control bleeding within 7 days post-epicardial surgical procedure or surgery to control bleeding within 7 days post-endocardial ablation procedure, if related to an AtriCure device or to the procedure;
 - ii. receipt of \geq 2 units of blood transfused in a 24-hour period during the first 7 days post epicardial surgical procedure or within the first 7 days post-endocardial ablation procedure, if related to the device or procedure;
 - iii. conversion to sternotomy or thoracotomy that requires \geq 2 units blood to be transfused or that is triggered by hypotension, cardiac arrest, or repair of a cardiac injury
- h. wound infection at surgical site requiring re-operation for wound debridement
- i. atrio-esophageal fistula (from the time of surgical procedure through 12-month follow-up visit)
- j. permanent phrenic nerve paralysis, defined as paralysis that remains unresolved at the 12-month follow-up visit
- k. permanent pacemaker implantation that is a direct result of injury to the specialized conduction system (SA node or AV node) during the epicardial surgical ablation procedure
- l. pulmonary vein (PV) Stenosis of $>70\%$, as measured at any time after the catheter ablation procedure through the 12-month follow-up visit
- m. major vascular access complications, including development of a hematoma, an arteriovenous fistula, or pseudoaneurysm that requires surgical intervention or transfusion, or that prolong hospital stay, or require a new hospital admission

9.3 Sample Size and Power

This study is powered for the primary effectiveness and primary safety endpoints. Both of these endpoints are compared to objective performance criteria, as a single-arm study has been determined to be the least burdensome and most appropriate approach. As with the FDA heart valve guidance document²⁰, this is justified by the extensive reporting in the literature of treatment outcomes for AF. Though catheter ablation would be the most natural comparison, no catheter ablation device has yet been approved for the persistent or longstanding persistent AF population. It is known that the rates of long-term effectiveness after catheter ablation in persistent and longstanding persistent AF patients are lower than in paroxysmal AF patients²¹. Similarly, adverse device effect (ADE) rates are likely higher in persistent populations due to the fact that these patients tend to be older, have longer AF history, and have more congestive heart failure than paroxysmal populations²². Thus, studies reporting results for aggregated AF populations tend to

be more favorable than what is seen in strictly persistent populations.

Based on the premises delineated above, the sample size calculations for powering the two primary endpoints are given in the following sections.

Effectiveness

The 12-month effectiveness rates after various dual/hybrid surgical epicardial procedures reported in the published literature vary widely, as most are from single center studies with varying procedural techniques and varying degrees of rhythm monitoring^{23, 24, 25, 26, 27, 28, 29}. Some sites reported on surgical-only procedures, others on concomitant epicardial/endocardial procedures, staged 2-part procedures, and combinations of these designs. Based on a detailed review of this literature and the two feasibility studies performed with the AtriCure Bipolar System, the lead investigators for this study believe that a 70% effectiveness rate after 12 months of follow-up is a reasonable estimate for the primary success endpoint.

While estimates of effectiveness success after catheter ablation also vary widely, primarily due to length of follow-up, severity of AF, and the definition of failure utilized, the overall success in a persistent population at 12 months, as defined by current guidelines, is believed to be less than 60%. In particular, the only regulatory trial for catheter ablation of atrial fibrillation with posted trial results, the Medtronic Ablation Frontiers TTOP trial, which utilized a similar population with a less stringent endpoint of a 90% reduction in AF after only 6 months of follow-up 3 months beyond the blanking period), had a success rate of 55.8%^{30, 31, 32}. A recent study in Spain (SARA) reported that 60.2% (59 of 98) of persistent AF patients (where LS persistent patients were excluded) were free of any recurrence of >30 s at 12 months follow-up³³. A report of 5-year outcomes in a LS persistent AF population of 202 patients showed that 35% remained in SR at 1 year after a single catheter ablation and 58% remained in SR at 1 year after multiple procedures, with persistent AF duration a highly significant predictor of relapse³⁴.

Based on a thorough review of the literature, an OPC of 60% success was chosen as the acceptable lower confidence limit for effectiveness in the combined persistent and LS persistent populations of this study. Thus, the goal for the primary effectiveness endpoint is to establish that the DEEP procedure significantly increases effectiveness relative to an OPC of a 60% catheter ablation success rate. Using the expected effectiveness success rate of 70% for the DEEP procedure, a one-sided alpha=0.025 level of significance, and a normal approximation to the binomial distribution with continuity correction, a sample size of N=182 is required to ensure 80% power.

Safety

Due to the groundbreaking new procedure that will be utilized in this trial, there are no regulatory trials with reported safety results for any type of similar minimally invasive procedure. The published literature for similar procedures is sparse and safety events are not reported with any consistency. Thus, the only realistic estimate of safety event rates is derived from the most recent feasibility trial. Based on this trial, a best estimate of the primary safety event rate over the dual procedures is 19%.

Patients with persistent AF are at increased risk of ischemic stroke and heart failure, while they may also be at increased risk of hemorrhagic stroke due to oral anticoagulation. In addition, their quality of life and ability of work can be greatly affected by both the disease and by the medications

used to treat the disease. All of the patients in this study will have tried and failed at least one treatment and many have failed several treatments, whether multiple AADs or AADs and catheter ablation.

The patients themselves and their treating physicians are willing to tolerate a substantial level of risk, if the reward is a similarly substantial level of benefit. The tolerable risk level, from the perspective of both the patients and the treating physicians, is related more to the subset of events that would cause permanent damage (i.e., death, stroke, MI, permanent and significant phrenic nerve damage) than to the overall level of procedure-related SAEs. It is believed that the rate of this subset of events will be quite low in the proposed study and that the benefit to the patient in terms of AF reduction or resolution, substantially reduced stroke risk, heart failure risk, and bleeding risk, and a substantial increase in quality of life will be the expected benefits.

There have been no regulated trials in this persistent AF population for a treatment that has produced the magnitude of benefit expected in this trial, and thus there is no comparable published standard for acceptable risk in relation to benefit. Rather, the acceptable risk level is proportionate to a patient's current risk profile and quality of life, based on their AF, and the anticipated level of benefit from the proposed treatment.

For these reasons, the clinicians involved in this study have agreed that a 28% rate of safety events, as specifically defined in the primary safety endpoint, and with the expected mix of permanent vs. resolvable events, is an acceptable risk level in relation to the expected benefits of this treatment.

In order to have an 80% chance of showing that the DEEP procedure has a primary safety event rate of <28% (UCL) when the actual underlying rate is 19%, a sample size of N=192 subjects is required. This sample size calculation is based on a one-sided $\alpha=0.025$ level of significance and assumes a normal approximation to the binomial distribution with continuity correction.

Overall Sample Size

The primary effectiveness and safety endpoints require similar numbers of patients, with the effectiveness endpoint driving the overall sample size. Due to the potential for significant loss to follow-up prior to the primary effectiveness endpoint at 12 months. In order to allow for an attrition rate of approximately 20%, this study will treat up to 220 subjects.

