9.7.1 Primary Analyses

Primary Safety

The statistical analysis of the primary safety endpoint will consist of a comparison of the proportion of patients who fail to complete the trial without a primary safety endpoint event to a historical control rate that is based on results from the feasibility trials. Adverse events will be adjudicated in accordance with section 12.1. The proportion of primary safety failures will be calculated with subjects as the experimental unit (i.e., the subject will be considered a failure if a primary safety event was experienced within the timeframes defined in the endpoint). The numerator of the proportion will be the number of subjects who have a primary safety event, and the denominator will be the total number of subjects.

A normal approximation to the binomial distribution, Z-test will be conducted at a one-sided $\alpha=0.025$ level of significance to test the following hypothesis that the proportion of failures is significantly lower than the OPC:

$$H_o : p_s \geq 0.28 \quad vs. \quad H_a : p_s < 0.28$$

where p_s = the proportion of primary safety failures in the safety population. The safety population will be the primary population for this analysis. Missing values will be treated as described in the Missing Values section below.

Primary Effectiveness

The statistical analysis of the primary effectiveness endpoint will consist of a comparison of the proportion of patients who remain a primary effectiveness success at the 12-month visit to a historical control rate that is based on results from the feasibility trials and published literature. The proportion of primary effectiveness successes will be calculated with subjects as the experimental unit (i.e., the subject will be considered a success if no primary effectiveness failure was recorded from the 6-month visit through the 12-month visit). The numerator of the proportion will be the number of subjects who are a primary effectiveness success, and the denominator will be the total number of subjects.

An exact, one-sample binomial test will be conducted at a one-sided $\alpha=0.025$ level of significance to test the following hypothesis that the proportion of effectiveness successes is significantly higher than the OPC:

$$H_o : p_E \leq .60 \quad vs. \quad H_a : p_E > .60$$

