9.9 Missing Endpoints

All safety analysis will utilize the safety population and no missing values will be imputed unless a subject misses a follow-up visit and cannot subsequently be contacted to determine their primary safety status. In this case, the primary safety endpoint will be considered a failure and the subject will be excluded from any subsequent secondary safety analyses for which their status is unknown. If a procedure is aborted due to a primary safety event, the subject will be considered a safety failure. If a subject misses a follow up visit, but it can be subsequently verified that the subject did not incur a safety failure, the subject will be considered a success.

The primary effectiveness analysis will utilize the ITT population and the LOCF method for missing values, as defined below. A subject with any primary effectiveness failure from the 6-month visit through the 12-month visit will be considered a failure for all methods below. Any subjects who withdraw or are lost-to-follow-up prior to the 12-month follow-up visit, or for any reason do not have 12-month ECG readings available, will be analyzed as follows:

- 1) **Last observation carried forward (LOCF):** Any subject who is missing a scheduled testing will be considered an effectiveness success or failure at that scheduled visit based on their status up to and including their last testing.
- 2) **Worst case:** Any subject with no primary effectiveness failure recorded and with no 12-month test data will be considered a failure.
- 3) **Best case:** Any subject with no primary effectiveness failure recorded and with no 12-month test data will be considered a success.
- 4) **Break-even:** If the study endpoint is met using the best-case methodology and is not met using the worst-case methodology, a break-even analysis will be performed to determine the number of subjects with missing endpoint data who would be required to be a success in order

to meet the endpoint.

All secondary endpoints for LAA exclusion will utilize the LOCF method for missing values. No missing values will be imputed for the remaining secondary endpoints. If a subject is missing a value for one of these secondary endpoints, they will not be included in the analysis of that endpoint. The number of patients with non-missing values will be reported for each endpoint.

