2.1.5 Secondary Health Economics Endpoints

All health economics endpoints are exploratory in nature.

1. Utilization of cardioversion, defined as the number of cardioversion events (visits) that a subject had in the past 12-month period. This endpoint will be measured at the 12-month, 2, 3, 4, and 5-year (Visits 11- 15) follow-up visits.
2. Hospital readmissions for AF, atrial flutter, or atrial tachycardia, defined as the number of readmissions in the past 12-month period. This endpoint will be measured at the 12-month, 2, 3, 4, and 5-year (Visits 11- 15) follow-up visits.
3. Total length of stay for all hospital readmissions for AF, atrial flutter, or atrial tachycardia, defined as the sum of the length of stay for each such visit within the last 12-month period. This endpoint will be measured at the 12-month, 2, 3, 4, and 5-year (Visits 11-15) follow-up visits.
4. Emergency Room Visits for AF, atrial flutter, or atrial tachycardia, defined as the number of visits in the past 12-month period. This endpoint will be measured at the 12-month, 2, 3, 4, and 5-year (Visits 11-15) follow-up visits.

Statistical Analysis Plan		Page 10 of 22
Sponsor	Study	Version
AtriCure	DEEP Pivotal Study	Version 2.0

3 Study Design

The study is a prospective, multicenter, single arm, pivotal study.

4 Sample Size Determination

The study is planned for up to 220 subjects and up to 35 sites (30 US and 5 OUS). Details regarding sample size determination are provided in the CSP.

5 Statistical Analyses

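### The effectiveness sample size of 182 omits the continuity correction it claims (with it, 192), and 220 treated does not cover a 20% loss

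*Protocol*

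**What the plan says.** Protocol 9.3 sets the effectiveness comparison at a 60% performance criterion against an expected 70% success rate, one-sided alpha 0.025. It then says that with a "normal approximation to the binomial distribution with continuity correction, a sample size of N=182 is required to ensure 80% power".

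The safety paragraph of the same section (28% criterion, 19% expected, one-sided alpha 0.025, 80% power) states that "a sample size of N=192 subjects is required" and that the calculation "assumes a normal approximation to the binomial distribution with continuity correction". The two endpoints therefore carry the same method label.

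Under Overall Sample Size, the protocol says that effectiveness determines the total, gives as its reason "Due to the potential for significant loss to follow-up prior to the primary effectiveness endpoint at 12 months", and concludes: "In order to allow for an attrition rate of approximately 20%, this study will treat up to 220 subjects".

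For the analysis, Protocol 9.7.1 says "An exact, one-sample binomial test will be conducted", and Protocol 9.9 says "The primary effectiveness analysis will utilize the ITT population and the LOCF method for missing values". SAP section 4 adds no calculation: "Details regarding sample size determination are provided in the CSP".

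**The concern.** Every input to the effectiveness calculation is printed, so the stated method should return the stated number. It returns 192, not 182. The attrition sentence has a separate problem: an allowance for 20% loss should leave at least the required number after 20% of the treated subjects are removed, and 220 does not.

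Because the SAP refers back to the protocol, section 9.3 is the only sample-size justification for the primary effectiveness endpoint of a study meant to support a PMA submission. Anyone who repeats the calculation as described will find that neither the 80% power at 182 nor the 20% cover can be reproduced. At stake is whether the stated power and attrition allowance can be relied on. The validity of the test is not in question.

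**Working it through.** **Inputs (Protocol 9.3).** Effectiveness: p0 = 0.60, p1 = 0.70, one-sided alpha 0.025 (z = 1.960), power 80% (z = 0.8416). Safety: p0 = 0.28, p1 = 0.19, same alpha and power. Treated: up to 220. Attrition: about 20%.

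**Formulas (one-sample normal approximation), with d = |p1 − p0|.**

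- Uncorrected: n = [1.960·√(p0(1−p0)) + 0.8416·√(p1(1−p1))]² / d²
- Continuity-corrected: n_cc = (n/4)·[1 + √(1 + 2/(n·d))]²

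**Step 1. Reproduce 182.** n = [(1.960·√0.24 + 0.8416·√0.21)/0.10]² = 181.13, rounded up to 182. This is the protocol's figure, reached without the correction.

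**Step 2. Apply the stated method.** n_cc = (181.13/4)·[1 + √(1 + 2/(181.13·0.10))]² = 191.003, rounded up to 192. Other corrected versions were tried: null variance only gives 199, alternative variance only gives 175, and the simple n + 1/d correction gives 191.13, rounded up to 192. None gives 182.

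**Step 3. Check against safety.** Uncorrected n = 180.81, rounded up to 181. Corrected n_cc = 191.76, rounded up to 192, which is the protocol's safety figure. The correction was applied to safety and not to effectiveness.

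**Step 4. Power for effectiveness.** The normal-approximation power is Φ[(d − c − 1.960·√(p0(1−p0)/N)) / √(p1(1−p1)/N)], with c = 1/(2N) if corrected and 0 if not. The exact column is the binomial test of Protocol 9.7.1 at one-sided 0.025.

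| N | Corrected | Uncorrected | Exact (successes needed) |
|---|---|---|---|
| 176 | 76.3% | 78.8% | 78.2% (119) |
| 182 | 77.9% | 80.2% | 78.7% (123) |
| 192 | 80.2% | 82.3% | 82.4% (129) |
| 220 | 85.7% | 87.3% | 86.5% (147) |

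Exact power moves in a sawtooth, so a single N should not be over-read. Over N = 177 to 187 it runs from 76.6% to 80.6%, with mean 78.7%. It first reaches 80% at N = 181 and stays at or above 80% only from N = 195.

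**Step 5. Attrition.**

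- 20% of 220 is 44, and 220 × 0.80 = 176, below 182 and 192.
- Loss that 220 covers: 1 − 182/220 = 17.3% (38 subjects), or 1 − 192/220 = 12.7% (28 subjects).
- Treated number needed for a 20% loss: 182/0.80 = 227.5, so 228; or 192/0.80 = 240.
- 182 × 1.20 = 218.4, close to 220. This suggests that the requirement was multiplied by 1.2 instead of divided by 0.8. That origin is an inference; the shortfall does not depend on it.

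**The case against.** The strongest reply is that nothing of consequence changes. The trial treats up to 220, more than the corrected 192, and exact power with all 220 evaluable is 86.5%. This stands, and it is why the remedy is confined to wording.

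On attrition, the protocol says approximately 20%, and 220 is a 20.9% uplift on 182 (220/182 = 1.209). Read as loss from those treated, the shortfall against 182 is 6 subjects, costing about half a point of exact power (78.7% to 78.2%). If 182 is kept and relabelled, 17% is a mild departure from 20%. Under the method the protocol actually names, however, the cover is about 13%, which approximately 20% does not describe.

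It is also fair that 176 is a worst case. The protocol's primary analysis keeps dropouts in the ITT denominator by LOCF, and the SAP's mITT population (SAP 5.2) removes only subjects without effectiveness data after the second blanking period. This limits the consequence but does not make the attrition sentence correct.

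Finally, 192 rests on strict rounding up: the corrected n is 191.003, and corrected power at 191 is 79.999%. Whether one writes 191 or 192, the answer is not 182.

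**Conclusion.** Both statements are wrong as written. The figure of 182 is the uncorrected result under a continuity-corrected label; the named method gives 192. The 220 treated covers a loss of 17.3% from 182 or 12.7% from 192, depending on which requirement is kept, and in neither case 20%.

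The size is modest. At 182, power is 2.1 points below 80% by the stated method and 1.3 points below under the protocol's exact test. If a full 20% were non-evaluable, exact power would be 78.2%. Type I error and the success rule are unaffected. These figures assume the protocol's own 60% and 70% rates and, for exact power, the test in Protocol 9.7.1. SAP 5.6.1.1 names a one-sided chi-squared test instead, and no claim is made here about its power. The point should be corrected because the SAP offers no other justification.

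**What to change.** Keep 220, the tests and alpha. Amend Protocol 9.3 in one of two consistent ways:

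- **State 192 with continuity correction** for effectiveness, and give the attrition allowance as about 13%. Both endpoints then rest on the same method and the same requirement.
- **Keep 182, labelled as without continuity correction**, and give the allowance as about 17%. The remark that effectiveness drives the total would then need explaining, since the stated safety requirement of 192 is larger before attrition.

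Instead of restating the allowance, the protocol could keep the 20% scenario and disclose that exact power is about 78% if a full 20% are non-evaluable (N = 176). That wording should name the test, because the protocol and SAP specify different ones.

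The cost is wording in Protocol 9.3 only, with no extra patients. The one drawback is that the stated attrition allowance or power looks slightly less favourable.
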